#### 6.5.1.4. Severe COVID-19

The incidence of the first severe COVID-19 starting 14 days after the second dose and after the third dose of IP. Severe COVID-19 is defined as COVID-19 (as defined above in [Section 6.5.1.3](#)) in conjunction with any of the following:

- Clinical signs indicative of severe systemic illness, respiratory rate  $\geq$  30 per minute, heart rate  $\geq$  125 beats per minute, oxygen saturation (SpO2)  $\leq$  93% on room air at sea level, or partial pressure of oxygen (PaO2)/fraction of inspired oxygen (FIO2)  $<$  300 mm Hg, OR
- Respiratory failure or ARDS, defined as needing high-flow oxygen, noninvasive or mechanical ventilation, or extracorporeal membrane oxygenation) or evidence of

Confidential

shock (systolic blood pressure < 90 mm Hg, diastolic BP < 60 mm Hg, or requiring vasopressors), OR

- Significant acute renal, hepatic, or neurologic dysfunction, OR
- Admission to an intensive care unit or death

For Part A, the time to the first occurrence of severe COVID-19 will be calculated as:

Time to the first occurrence of severe COVID-19 = Date of documented severe COVID-19 – Date of first study dose + 1.

For Part B, the time to the first documented SARS-CoV-2 infection will be calculated as:

Time to the first occurrence of severe COVID-19 = Date of documented severe COVID-19 – Date of BD + 1.

Cases will be counted starting 14 days after the second dose, third dose, and BD, e.g., date of documented Severe COVID-19 – Date of second/third dose/BD  $\geq$  14.

#### **6.5.1.5. Secondary Case Definition of COVID-19**

The incidence of the first secondary COVID-19 starting 14 days after the second dose and after the third dose of IP. The secondary case definition of COVID-19 is defined as one of these following systemic symptoms:

- Fever (temperature  $\geq 38^{\circ}\text{C}$ ) or chills, cough, shortness of breath or difficulty breathing, fatigue, muscle aches or body aches, headache, new loss of taste or smell, sore throat, nasal congestion or rhinorrhea, nausea or vomiting or diarrhea AND
- A positive NP swab, nasal swab, or saliva sample (or respiratory sample, if hospitalized) for SARS-CoV-2 by RT-PCR.

For Part A, the time to the first occurrence of secondary COVID-19 will be calculated as:

The time to the first occurrence of secondary COVID-19 = Date of documented secondary COVID-19 – Date of first study dose + 1.

For Part B, the time to the first occurrence of secondary COVID-19 will be calculated as:

The time to the first occurrence of secondary COVID-19 = Date of documented secondary COVID-19 – Date of BD + 1.

Confidential

Cases will be counted starting 14 days after the second dose, third dose, and BD, e.g., date of documented secondary COVID-19 – Date of second/third dose/BD  $\geq$  14.

### 6.5.2. Analysis of Infection Rates

For Part A and Part B, the number and percentage of subjects experiencing each of the infection events below will be summarized by participant group for the mITT Set:

- SARS-CoV-2 infection
- Asymptomatic SARS-CoV-2
- COVID-19
- Severe COVID-19
- Secondary case definition of COVID-19

For each of these summaries, the incidence rate (i.e. the infection rate) will be provided by participant group, calculated as the number of cases divided by the total person-time. The 95% CI of the incidence rate will be calculated using the exact method (Poisson distribution) and adjusted by person-time.

Person-time is defined as the total time from first dose of each part of the study (Part A or Part B) to the earliest of the following dates: date of event, dose date in next part, last date of study participation, censoring time, or efficacy data cutoff date.

For participants who are a case for symptomatic COVID-19, symptoms reported by these participants will be summarized.

For SARS-CoV-2 infection, asymptomatic SARS-CoV-2 infection, COVID-19, and severe COVID-19, the timeframe for the counting cases will begin at 14 days after the last planned dose and will differ by study arm:

- 2-dose unvaccinated without booster: from day 43 up to and including day 394,
- 3-dose unvaccinated without booster: from day 99 up to and including day 450,
- 3-dose previously vaccinated with Moderna COVID-19 vaccine without booster: from day 15 up to and including day 365.
- 2-dose unvaccinated with booster: from BD-Day 1 + 14 up to and including BD-Day 181.

Confidential

- 3-dose unvaccinated with booster: from BD-Day 1 + 14 up to and including BD-Day 181)
- 3-dose previously vaccinated with Moderna COVID-19 vaccine with booster: from BD-Day 1+ 14 up to and including BD-Day 181 .
- 3-dose previously vaccinated with mRNA or non-mRNA COVID-19 vaccine with booster: from BD-Day 1 + 14 up to and including BD-Day 181.

In addition, the COVID-19 and SARS-CoV-2 infection endpoints may be also analyzed by specimen types (i.e. NP swab, nasal swab, or saliva samples), calendar months, time periods, and all types of the diagnostic test (i.e., both RT-PCR results and other COVID-19 test results). The number and percentage of subjects experiencing COVID-19 may be summarized by specific variant groups. Listings of serum nAb and bAb levels against SARS-CoV-2, solicited ARs and unsolicited AEs will be provided for subjects infected by SARS-CoV-2.

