From unvaccinated participants who receive 2 doses of vaccine (healthy adults [Group A5] and SOT recipients who decline to receive a third dose [Group A1]), blood samples will be collected at baseline (Day 1), Day 29 (28 days after dose 1), Day 57 (28 days after dose 2), Day 209 (6 months after dose 2), and Day 394 (12 months after dose 2).

From previously vaccinated SOT participants who receive 1 dose of mRNA-1273 (Group A3), blood samples will be collected at pre-dose 3 (Day 1), Day 29 (28 days after dose 3), Day 180 (6 months after dose 3), and Day 365 (12 months after dose 3).

These blood samples will be for the assessment of the following endpoints and analytes:

- Measurement of SARS-CoV-2-specific bAb and nAb responses

- Development of Ab directed against nonvaccine antigen (nucleocapsid protein), which will signify infection with SARS-CoV-2. Participants who tested positive for Ab against SARS-CoV-2 nucleocapsid protein at baseline can continue in the study.

From unvaccinated SOT participants (Group A1 and Group A2), blood samples for cell-mediated immunity (CMI) studies will also be collected at Day 1, Day 36, and Day 92 (SOT recipients receiving 3 doses [Group A2]) from a subset of up to 50 SOT participants, as well as, from 20 healthy controls (Group A5) (Day 1 and Day 36), and from a subset of at least 50 previously vaccinated SOT recipients (Group A3) at Day 1 and Day 8, for exploratory assessments to characterize T- and B-cell responses to vaccine.

The NP swab samples obtained at illness visits ([Section 7.3.1](#)) will be used as sources of SARS-CoV-2 for genetic sequencing.

SARS-CoV-2 bAb against the nonvaccine antigen (nucleocapsid protein) will also be collected at the Illness and Convalescent visits.

The number of cases of COVID-19 will be assessed throughout the study ([Section Error! Reference source not found.](#)). Once a participant is identified as a case of COVID-19, a convalescent visit will be scheduled approximately 28 days after the confirmed diagnosis for a clinical evaluation and immunologic assessment of SARS-CoV-2 infection.

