5.4. Study Treatment Compliance

All doses of vaccine will be administered at the study site under direct observation of medically qualified study staff and appropriately recorded (date and time) in the eCRF. Qualified study site staff will confirm that the participant has received the entire dose of vaccine. If a participant does not receive vaccine or does not receive all of the planned doses, the reason for the missed dose will be recorded. Data will be reconciled with study site accountability records to assess compliance.

Participants who miss the second or third dose due to noncompliance with the visit schedule and not due to a safety pause will still be required to follow the original visit and testing schedule as described in the protocol and their regimen schedule. Unless consent is withdrawn, a participant who withdraws or is withheld from receiving the second or third dose will remain in the study and complete all safety and immunogenicity assessments required through the participant's last scheduled study visit.

The study site staff are responsible for ensuring that participants comply with the allowed study visit windows. If a participant misses a visit, every effort should be made to contact the participant and complete a visit within the defined visit window ([Section 10.1](#)). If a participant does not complete a visit within the time window, that visit will be classified as a protocol deviation. The participant will continue with subsequent scheduled study visits. All safety requirements of the missed visit will be captured and included in the subsequent visit.

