- Imputation rules for missing AE dates are provided in [Appendix C](#).
- For laboratory assessments, if the majority of results are indefinite, imputation of these values will be considered. If the laboratory results are reported as below the LLOQ (e.g., <0.1), the numeric values will be imputed by  $0.5 \times \text{LLOQ}$  in the summary. If the laboratory results are reported as greater than the ULOQ (e.g., >3000), the numeric values will be imputed by ULOQ in the summary.
- For immunogenicity assessments, imputation of missing results will be considered based on description in [Section 6.4](#).
- Other incomplete/missing data will not be imputed, unless specified otherwise.

**Participant groups** will be summarized according to the schema below.

- Transplant status:
  - SOT Kidney
  - SOT Liver
  - SOT Total
  - 2-Dose Healthy
- Dosing regimens:
  - Overall
  - Unvaccinated SOTs Who Received 2 Doses
  - Unvaccinated SOTs Who Received 3 Doses
  - Previously Vaccinated SOTs Who Received a Third Dose
  - Total SOTs Who Received 3 Doses
  - Primary Series All SOTs Who Received a Booster Dose
- Primary Series All SOTs Who Received a Booster Dose:
  - Overall
  - 3-Dose Moderna
  - 3-Dose Pfizer

Confidential

- Other

Unless otherwise mentioned, the results of the analyses will be summarized according to the participant groups above. Subjects under the same dosing regimen may be combined for analyses regardless of BD. Participants that received booster may be analyzed separately from participants that did not receive booster.

**Subgroup analyses** for safety and immunogenicity endpoints may be analyzed in select subgroups specified below as applicable:

- Age (18 to < 65,  $\geq$  65)
- Time of post-transplantation (< 2,  $\geq$  2 years)
- Baseline SARS-CoV-2 Status in each part (Positive, Negative) (for safety data)
- Sex (Male, Female)
- Race (White, Communities of color)
- Anti-metabolite immunosuppression (Yes, No)
- Combination of immunosuppressants (Mycophenolate, Tacrolimus, and Prednisone; Mycophenolate and Tacrolimus; Tacrolimus; and Other)
- Previous induction therapy (Basiliximab or other monoclonal antibody; Basiliximab or other monoclonal antibody with steroids; Thymoglobulin; Thymoglobulin with steroids; or steroids alone)

All analyses will be conducted using SAS Version 9.4 or higher.

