**Table 1. Derivation for SARS-CoV-2 Infection**

Baseline SARS-CoV-2 Status	Post-baseline assessments		Endpoint: SARS-CoV-2 infection
	RT-PCR test post-baseline	bAb levels against SARS-CoV-2 Nucleocapsid	
Negative at Baseline of each part	Positive (either at scheduled NP swab test, or at symptom-prompt NP swab test 14 days after the second/third dose)		Case
Negative at Baseline of each part		Positive (28 days after the second, third dose, and BD or later) as measured by Roche Elecsys	Case

The date of documented infection will be the earlier of:

- Date of positive post-baseline RT-PCR result, or
- Date of positive post-baseline serology test result based on bAb specific to SARS-CoV-2 nucleocapsid

For Part A, the time to the first documented SARS-CoV-2 infection will be calculated as:

Time to the first SARS-CoV-2 infection = Date of the first infection – Date of first study dose + 1.

For Part B, the time to the first documented SARS-CoV-2 infection will be calculated as:

Time to the first SARS-CoV-2 infection = Date of the first infection – Date of BD + 1.

Cases will be counted starting 14 days after the second, third dose, and BD, e.g., date of documented infection - Date of the second/third dose/BD  $\geq$  14.

Confidential

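### SAP 6.5.2 starts person-time at the first dose of each part but counts cases only from 14 days after the last planned dose, so incidence rates and Poisson limits for the RT-PCR-based endpoints are too low, and unequally so across Part A groups.

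*SAP*

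**What the plan says.** SAP 6.5.2 reports, by participant group in the mITT Set, the number and percentage of subjects with each of five infection endpoints. It adds an incidence rate (cases over total person-time) with an exact Poisson 95% interval. The denominator is defined thus: "Person-time is defined as the total time from first dose of each part of the study (Part A or Part B) to the earliest", after which it lists the possible end dates: event, next-part dose, last day in the study, a censoring time and the data cutoff.

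The numerator starts later. For four of the five endpoints, 6.5.2 says "the timeframe for the counting cases will begin at 14 days after the last planned dose and will differ by study arm". The listed starts are Day 43 (2-dose), Day 99 ("3-dose unvaccinated without booster: from day 99 up to and including day 450"), Day 15 (previously vaccinated with Moderna) and 14 days after BD-Day 1 (every booster group). The secondary case definition is not named in that sentence, but 6.5.1.5 gives it a similar start: "Cases will be counted starting 14 days after the second dose, third dose, and BD".

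SAP 6.5, 6.5.1 and 6.5.2 contain no rule that removes the days before the window from person-time. The SAP also does not say what happens to a participant who has an event before the window opens. SAP 5.2 keeps participants who go on to Part B in the Part A analysis sets, but 6.5.2 lists no Part A counting window for them.

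**The concern.** An incidence rate is interpretable when the same days feed the numerator and the denominator. Here the denominator holds an opening stretch in which, by definition, no RT-PCR-based case can be counted. This lowers the rate and scales down both Poisson limits by the same factor. With no cases the point estimate stays at zero, but the upper limit is still too low, which reads as more reassuring than the data allow.

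The stretch differs by group: 98 days for the 3-dose unvaccinated group and 14 for the previously vaccinated group. Neighbouring columns of one table would therefore carry different built-in shortfalls. Part A incidence of COVID-19 is a secondary objective (SAP 2.2), and in an estimation study the reported rates are the result.

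**Working it through.** **Reproducing the plan's starts.** The last planned dose day + 14 gives 29 + 14 = 43, 85 + 14 = 99 and 1 + 14 = 15, as 6.5.2 states. The SAP gives no expected rate or case count to reproduce.

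**Formulas.** Uncountable share = (start day − 1) / last day. The rate and both Poisson limits are too low by that share. Aligning the start multiplies them by last day / (last day − start day + 1).

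**Inputs.** Starts and ends come from SAP 6.5.2. Scheduled booster days are from Protocol Table 10: D149 healthy, D205 3-dose, D120 previously vaccinated. The booster rows end Part A time the day before and assume the same counting starts.

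| Group | Start | Last day | Too low by | After alignment |
|---|---|---|---|---|
| 2-dose, no booster | 43 | 394 | 42/394 = 10.7% | 394/352 = 1.119 |
| 3-dose unvaccinated, no booster | 99 | 450 | 98/450 = 21.8% | 450/352 = 1.278 |
| Same, counting from dose 2 + 14 | 43 | 450 | 42/450 = 9.3% | 450/408 = 1.103 |
| Previously vaccinated, no booster | 15 | 365 | 14/365 = 3.8% | 365/351 = 1.040 |
| Part B, every group | 15 | 181 | 14/181 = 7.7% | 181/167 = 1.084 |
| Healthy, Part A cut at booster | 43 | 148 | 42/148 = 28.4% | 148/106 = 1.396 |
| 3-dose unvaccinated, cut at booster | 99 | 204 | 98/204 = 48.0% | 204/106 = 1.925 |
| Previously vaccinated, cut at booster | 15 | 119 | 14/119 = 11.8% | 119/105 = 1.133 |

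The third row is there because SAP 6.5 and 6.5.1 speak of 14 days after the second and third doses, which can be read as counting 3-dose cases from Day 43. On that reading the 3-dose figure cut at the booster is 42/204 = 20.6%. Protocol 3.1.1 puts the healthy booster at Day 129 rather than D149. That would give 42/128 = 32.8%, and the two passages need reconciling.

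**Apparent ratio, previously vaccinated to 3-dose unvaccinated, at equal hazards.**
- Unboosted: (351/365)/(352/450) = 1.23.
- Unboosted, other reading: (351/365)/(408/450) = 1.06.
- Both cut at the booster: (105/119)/(106/204) = 1.70; other reading: (105/119)/(162/204) = 1.11.

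**Effect on the limits.** Assume 50 unboosted 3-dose participants with full follow-up. Person-years are 50 × 450/365.25 = 61.6 as written and 50 × 352/365.25 = 48.2 aligned.
- Zero cases (Poisson upper limit 3.689): 5.99 as written against 7.66 aligned, per 100 person-years.
- Five cases (limits 1.623 and 11.668): 8.12 (2.64 to 18.94) as written against 10.38 (3.37 to 24.22) aligned.

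Stopping person-time at the event changes little. With an assumed constant hazard of 0.1 to 0.3 per year, the rate as written is 0.889 to 0.879 (2-dose), 0.774 to 0.757 (3-dose) and 0.960 to 0.956 (previously vaccinated) of the true one.

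**Serology.** SARS-CoV-2 infection and asymptomatic infection also count cases dated by the "Date of positive post-baseline serology test result based on bAb specific to SARS-CoV-2 nucleocapsid" (SAP Table 1). In the previously vaccinated group, "blood samples will be collected at pre-dose 3 (Day 1), Day 29 (28 days after dose 3"). A first positive at Day 29 can therefore reflect infection at any time since Day 1; the same holds for BD-Day 29 after BD-Day 1. Ignoring seroconversion lag, the serology component there is short by about 0. It is short by at most 28/394 = 7.1% (2-dose, previous sample Day 29) and 84/450 = 18.7% (3-dose, previous sample Day 85). A +14-day start would over-correct it by up to 4.0% in each Part A group (365/351, 366/352, 366/352) and 8.4% in Part B (181/167).

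**The case against.** The strongest reply is that little depends on these rates. Protocol 8.3.4 asks for counts and percentages, and for an infection rate only in the healthy arm; the by-group person-time rates are largely a SAP addition. No hypothesis is tested and no between-group comparison is planned. The groups are not randomised, and the previously vaccinated arm came in only with Amendment 3, so calendar exposure may differ. The denominator is stated openly, and in the five-case example the shift is small against the width of the interval.

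All of this limits the weight of the point, but none of it makes the rate correct. The censoring time in the definition can only end person-time; it cannot move the start. The objection that 21.8% depends on how the 3-dose window is read also stands. On the other reading most of the inequality with the 2-dose group disappears (9.3% against 10.7%), though the rate is still too low.

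A reader might infer three stronger things:
- That all five infection rates are understated alike. The serology dating rule does not support this.
- That previously vaccinated participants will be reported with a rate 1.23 times too high relative to the 3-dose group. That figure assumes equal hazards and no boosters and serves only as an illustration.
- That efficacy or immunogenicity conclusions are compromised. Primary endpoints, error rates, counts and percentages do not use this denominator.

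**Conclusion.** Wrong as written, and worth correcting before the analysis. For COVID-19, severe COVID-19 and the secondary case definition, the rate and its exact Poisson limits are too low in every group, with a shortfall that differs across Part A groups and is uniform within Part B.

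The size depends on two things the SAP leaves open: whether 3-dose cases count from dose 3 or dose 2, and how Part A time before a booster is windowed. For unboosted participants the shortfall runs from 3.8% to 21.8%. For participants boosted on schedule it reaches 48.0% in the 3-dose group, provided the same counting starts apply. The figures use planned visit days and full follow-up to the stated end; the realised values will depend on booster uptake, dropout and dose delays. The matter concerns descriptive estimates only.

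**What to change.** For the three RT-PCR-based endpoints:
- Start each participant's person-time on the first day a case of that endpoint can count: the actual date of the last dose that defines the group in that part (or the BD) + 14 days. Keep the stated end rule, and include only mITT participants still in follow-up on that day.
- Use one counting start, from actual dose dates, in 6.5.1 and 6.5.2. Apply it also to the secondary case definition and to the Part A time of participants later boosted. Nominal days will not do: Protocol 10.1 allows a 21-day extension, and Protocol 6.1.1 allows dosing later still once the participant is clinically stable.
- Say which dose sets the start when one is missed. Under Protocol 5.4 "a participant who withdraws or is withheld from receiving the second or third dose will remain in the study", and SAP 6.1 already names groups by doses received (for example "Unvaccinated SOTs Who Received 3 Doses"). A participant who skips dose 3 because of infection then falls in the 2-dose group, which should be noted.
- State one rule for participants who meet the same endpoint before the window, and apply it to both cases and person-time. Removing everyone with any documented infection would be too broad, because the rate and the percentage could then rest on different cases. Report the at-risk N and the cases beside each rate.

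For the two endpoints that include serology, do not impose the +14-day start. Keep their counts and percentages. Then either report the rate of the RT-PCR component on the aligned person-time, or state that the combined rate includes serology-dated cases that may have been acquired before the window.

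The cost is SAP wording and a small derivation on data already collected. Reported RT-PCR-based rates will rise by the factors in the table. The rate population will be slightly smaller than the mITT Set, by an amount the documents do not allow to be estimated; the at-risk N will show it.

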
 To describe the incidence of asymptomatic SARS-CoV-2 infection after mRNA-1273 vaccination in adult solid organ transplant (SOT) recipients and healthy adult participants with negative SARS-CoV-2 at baseline 	
 The incidence of asymptomatic SARS-CoV-2 infection among recipients of mRNA-1273 SARS-CoV-2 vaccine will be defined in participants with negative SARS-CoV-2 at baseline as bAb levels against SARS-CoV-2 nucleocapsid protein negative (as measured by Roche Elecsys) at Day 1 that become positive (as measured by Roche Elecsys) counted starting 28 days after the second dose and 28 days after the third dose of vaccine, OR Positive reverse transcriptase polymerase chain reaction (RT-PCR) counted starting 14 days after the second and after the third dose of vaccine

 To describe the incidence of coronavirus disease 2019 (COVID-19) after vaccination with mRNA-1273 in SOT recipients and healthy participants 	
 First occurrence of COVID-19 starting 14 days after the second dose and after the third dose of vaccine, where COVID-19 is defined as symptomatic disease based on the following criteria The participant must have experienced at least TWO of the following symptoms: fever ($\geq 38^{\circ}\text{C}/\geq 100.4^{\circ}\text{F}$), chills, myalgia, headache, sore throat, or new olfactory and taste disorder(s), OR The participant must have experienced at least ONE of the following respiratory signs/symptoms: cough, shortness of breath or difficulty breathing, OR clinical or

Objectives	Endpoints

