5.3.2. Administration of Study Vaccine

Each unvaccinated SOT and Healthy participant (Group A1Group A2, and Group A5) will receive two 100-µg doses of vaccine by IM injection, 28 days apart (ie, Day 1 and Day 29) into the deltoid

muscle, according to the procedures specified in the mRNA-1273-P304 Pharmacy Manual. Preferably, both doses should be administered into the same nondominant arm. Neither dose should be administered into an arm that contains an arteriovenous fistula. Unvaccinated SOT recipients will be offered to receive a third dose of vaccine (Group A2) on Day 85 (56 days after dose 2). Previously vaccinated SOT recipients (Group A3) will receive a single 100- μ g dose (dose 3) on Day 1. In Part B (Group B2, Group B3, Group B4, and Group B5), participants will receive a single 100- μ g dose on BD-D1. Under Amendment #4, unvaccinated SOT participants who will be enrolled will be given 3 100 μ g doses in Part A then proceed to Part B to receive a 100 μ g booster dose. Under Amendment #4, SOT participants previously vaccinated with 2 doses of Moderna COVID-19 vaccine outside of the study who will be enrolled will receive a third 100 μ g dose in Part A then proceed to Part B to receive a 100 μ g BD.

At each visit when vaccine is administered, participants will be monitored for a minimum of 30 minutes after administration. Assessments will include vital sign measurements and monitoring for local or systemic ARs.

Eligibility for a subsequent dose of vaccine will be determined by following the criteria outlined in [Section 6](#).

The study sites will be appropriately staffed with individuals with basic cardiopulmonary resuscitation training/certification. Either onsite resuscitation equipment and personnel or appropriate protocols for the rapid transport of participant to a resuscitation area or facility are required.

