## **6.5. COVID-19 and SARS-CoV-2 Infection Analysis**

For both Part A and Part B, the mITT Set (Part A/Part B) will be used for the analysis of COVID-19 and SARS-CoV-2 infection starting from 14 days after the second dose and third dose received for each participant group. The PP Set (Part A/Part B) may be used in the analyses as appropriate, unless otherwise specified.

**Baseline SARS-CoV-2 status and Pre-booster SARS-CoV-2 Status** is described in [Section 6.1](#). The serology test results based on Roche Elecsys assay at baseline, and the RT-PCR test results at baseline will be summarized by participant group.

Participants with pre-vaccination baseline positive or missing SARS-CoV-2 status will be excluded from the mITT Set (Part A) infection analysis.

Participants with pre-booster positive or missing SARS-CoV-2 status will be excluded from the mITT Set (Part B) infection analysis.

The post-baseline serology test results based on the Roche Elecsys assay and the RT-PCR test results will also be summarized by visit.

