### 6.5.1.3.COVID-19

The incidence of the first occurrence of COVID-19 starting 14 days after the second, third dose, and BD of IP will be presented. COVID-19 is defined as symptomatic disease based on the criteria specified in [Section 3.2.2](#). Cases are defined as participants meeting clinical criteria based on both symptoms for COVID-19 and positive RT-PCR test results.

Surveillance for COVID-19 symptoms will be conducted every two weeks by either telephone calls or eDiary prompts (alternating). Subjects reporting COVID-19 symptoms, as defined in Section 7.3.2 of Protocol Amendment 4, will be arranged an illness visit to collect an NP swab.

For this endpoint, a COVID-19 case will be identified as a positive post-baseline RT-PCR test result, together with eligible symptoms as described below in [Table 2](#).

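### For four infection endpoints, SAP 6.5.2 counts cases in unboosted Group A2 only from Day 99, so Days 43 to 98 fall in no listed window although person-time runs from the first dose

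*SAP*

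**What the plan says.** **Endpoint and derivation sections.** Protocol section 2 (Table 1) defines the COVID-19 endpoint as "First occurrence of COVID-19 starting 14 days after the second dose and after the third dose of vaccine", and SAP 3.2.2 repeats it. SAP 6.5 describes the infection analysis as "starting from 14 days after the second dose and third dose received for each participant group". SAP 6.5.1.3 adds: "The incidence of the first occurrence of COVID-19 starting 14 days after the second, third dose, and BD of IP will be presented". The derivations in 6.5.1.1 to 6.5.1.4 share one counting rule: the event date minus the date of the second dose, third dose or booster must be at least 14 days.

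**Analysis section.** For four endpoints (SARS-CoV-2 infection, asymptomatic infection, COVID-19, severe COVID-19), SAP 6.5.2 says that "the timeframe for the counting cases will begin at 14 days after the last planned dose and will differ by study arm". The two lists that matter here are "2-dose unvaccinated without booster: from day 43 up to and including day 394" and "3-dose unvaccinated without booster: from day 99 up to and including day 450". The same section starts person-time at the first dose of the study part, which is Day 1 in Part A.

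**Dosing.** Protocol 5.3.2 gives the first two doses "28 days apart (ie, Day 1 and Day 29", and the third to "Group A2) on Day 85 (56 days after dose 2".

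**The concern.** Read literally, the endpoint sections open counting for an A2 participant 14 days after dose 2, and 6.5.2 opens it 14 days after dose 3. A case documented between those two dates qualifies under 6.5.1 and is left out under 6.5.2. The Day 43 window is no help, because it is listed for the two-dose regimen, and SAP 6.1 treats the two regimens as separate participant groups.

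The study does look for infection in A2 during this period. Protocol Table 8 schedules a nasopharyngeal swab and nucleocapsid serology at Days 57 and 85, and SAP 6.5.1.1 names Day 57 seroconversion as a qualifying result. Two programmers following different sections could therefore produce different tables for secondary endpoints.

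The rate itself is also affected. Its denominator includes time before Day 99, when no case can enter the numerator. As written, the listed windows supply post-dose-2 cases among transplant recipients only from Group A1, those who took two doses.

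**Working it through.** **Inputs.** Dose 2 on Day 29 and dose 3 on Day 85 (protocol 5.3.2); lag of 14 days, and window ends of Day 394 and Day 450 (SAP 6.5.2); person-time from Day 1 (SAP 6.5.2); dose windows of -3/+7 days (protocol 3.1).

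**1. Reproduce the SAP's window starts** (day of last planned dose + 14).
- Two-dose: 29 + 14 = Day 43.
- Three-dose: 85 + 14 = Day 99.
- Previously vaccinated: 1 + 14 = Day 15.

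All three match 6.5.2.

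**2. Length of the gap in unboosted A2.**
- Day 43 to Day 98 inclusive: 98 - 43 + 1 = 56 days.
- Day 43 to Day 450: 450 - 43 + 1 = 408 days. Share: 56/408 = 0.137, about 14%.
- Day 99 to Day 450: 450 - 99 + 1 = 352 days.

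**3. Effect of the dose windows.** Dose 2 may fall on Days 26 to 36. Against a fixed Day 99 the gap is 99 - (36 + 14) = 49 to 99 - (26 + 14) = 59 days. Measured between actual doses, it is 82 - 36 = 46 to 92 - 26 = 66 days. A participant dosed at the late edge for dose 3 (Day 92) reaches Day 99 only 7 days after that dose.

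**4. Numerator against denominator**, for a participant followed event-free to Day 450, assuming a constant hazard.
- As written: countable days / person-days = 352/450 = 0.78.
- Counting from Day 43, with person-time still from Day 1: 408/450 = 0.91.
- Uncountable person-time as written: 98/450 = 0.218. The gap accounts for 56/450 = 0.124 and Days 1 to 42 for 42/450 = 0.093.

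**5. Possible number of cases.** The documents give no infection rate. With assumed rates of 0.05, 0.10, 0.20 and 0.40 per person-year, expected cases in the gap per 100 participants are 100 × rate × 56/365.25 = 0.8, 1.5, 3.1 and 6.1.

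**The case against.** The best defence is that second dose and third dose are meant respectively, by regimen. Protocol 7.3 does this for serology, starting at Day 57 for two doses and Day 113 for three, and 6.5.2 may simply be applying that pattern. The reading is possible. But neither the counting rule in SAP 6.5.1 nor the reference to each participant group in SAP 6.5 says so, and the passages still have to be reconciled. It also leaves the person-time mismatch untouched.

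Some of these infections appear elsewhere:
- The secondary case definition is not among the four restricted endpoints, and SAP 6.5.1.5 still counts it from 14 days after dose 2.
- Confirmed COVID-19 is recorded as a medically attended adverse event.
- Swab and serology results are summarised by visit.
- Protocol 8.3.4 plans a whole-study summary of infections, although the SAP does not carry it over. The SAP's analysis by time period is optional.

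These points stand, but none supplies the endpoint rate after dose 2.

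A reader might infer four stronger things that the documents do not support:
- **That every infection in the gap is lost.** One acquired late in the gap but first detected by serology at Day 113 is dated Day 113 and counted. The loss concerns infections documented on Days 43 to 98.
- **That the quoted line removes the period for the whole of A2.** It covers participants without a booster. Boosted A2 participants have a different listed window, which raises its own question.
- **That participants infected in the gap remain at risk from Day 99 as if uninfected.** SAP 6.5.2 defines no risk set opening on Day 99, and the endpoint is a first occurrence. The handling is unspecified.
- **That the benefit of the third dose can no longer be described.** Protocol 8.1 and SAP 4.2 plan estimation without between-group comparisons, so no such infection analysis exists to be lost.

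**Conclusion.** The conflict is real and should be resolved before database lock. For the four named endpoints in unboosted A2, infections documented in a 56-day period (49 to 59 days with the dose 2 window, against the fixed Day 99) have no listed window, although 3.2.2, 6.5 and 6.5.1 count them.

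The 0.78 ratio rests on a constant hazard and complete event-free follow-up to Day 450. It combines the gap with the earlier mismatch over Days 1 to 42, so the gap should not be blamed for all of it. A changing epidemic would move the figure either way. The number of cases at stake cannot be stated from the documents; the range of 0.8 to 6.1 per 100 participants depends wholly on the assumed rates. The consequence is confined to descriptive secondary endpoints.

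**What to change.** Reconcile SAP 6.5.2 with 3.2.2, 6.5 and 6.5.1 by giving A2 two windows, set from actual dose dates:

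1. **After dose 2:** from dose 2 + 14 days to dose 3 + 13 days, pooled with A1 in one column. Pooling matters: an A2-only column would condition on later receipt of dose 3.
2. **After dose 3:** from dose 3 + 14 days.

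Start person-time when each window opens. State that a participant with a documented infection before a window opens is excluded from both the first-occurrence numerator and the person-time of that window.

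If the by-regimen reading was intended, say so in 3.2.2, 6.5 and 6.5.1 and record it in SAP section 7, which at present lists no changes. Person-time would still need to start with the window.

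The cost is SAP wording, a revised person-time derivation and one extra table column. No new data are needed, since the dose dates, swabs, serology and symptom surveillance are already collected.
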